### **5.10.1.4 Deaths**

Listings of deaths will be provided.

### **5.10.1.5 Adverse Events of Special Interest**

Definition of adverse event of special interest (AESI) is referred to the Protocol section 8.2.2.1.

Below AESIs will be summarized in both TEAE and post-dose AE, respectively:

- AESIs by PT
- AESIs by SOC and PT
- AESIs by SOC, PT and maximum CTCAE grade

Listings of AESIs will be provided.

## **5.10.2 Laboratory Data**

Laboratory data of hematology, chemistry, and coagulation will be summarized for the actual value and the change from baseline value at each scheduled assessment. Besides, all data will be graded according to the NCI CTCAE Version 4.0, and summarized by baseline and maximum post-baseline CTCAE grade, including unscheduled visits. Shift tables will summarize the shift from baseline grade to maximum post-baseline CTCAE grade.

Listings of laboratory data of hematology, chemistry, and coagulation will be provided. In addition, listings of urinalysis and other test, if applicable, will also be provided.

### **5.10.3 Electrocardiogram**

Electrocardiogram (ECG) data will be summarized for the actual value and the change from baseline value at each scheduled assessment. Shift tables will summarize the shift from baseline to EOT and worst post baseline visit in ECG interpretation (categorized as normal; abnormal, not clinically significant; and abnormal, clinically significant).

Corrected QT interval by Fredericia (QTcF) will be summarized by categories as follows:

- QTcF interval > 450 ms
- QTcF interval > 480 ms
- QTcF interval > 500 ms
- QTcF interval increases from baseline > 30 ms
- QTcF interval increases from baseline > 60 ms

Listings of ECG data will be provided.

### **5.10.4 Vital Signs**

Vital sign data, including height and weight, will be summarized for the actual value and the change from baseline value at each scheduled assessment.

Listings of vital sign data, including height and weight, will be provided.

### **5.10.5 ECOG Performance Status**

ECOG performance status will be summarized at each scheduled assessment. Shift tables will summarize the shift from baseline to EOT and worst post baseline visit in ECOG performance status.

Listing of ECOG performance status will be provided.

### **5.10.6 Physical Examinations**

Listings of physical examinations will be provided.

### **5.10.7 Pregnancy Test**

Listings of pregnancy test, if applicable, will be provided.

## **5.11 Patient-Reported Outcomes**

Three PRO questionnaires will be assessed in Phase 2:

- European Organization for Research and Treatment of Cancer (EORTC) Quality of Life Questionnaire (QLQ)-Core 30 (C30),
- Lymphoma subscale (LymS) of Functional Assessment of Cancer Therapy – Lymphoma (FACT-Lym),
- EuroQoL-5 Dimensions-5 Levels (EQ-5D-5L).

Details are referred to the Protocol section 8.5.

Completion rate of each PRO questionnaire (completed questionnaires as a proportion of the expected) will be calculated. **Item level missing values will be imputed as per recommendation by the instrument developers.**

PRO scores for the five functional domains, eight symptoms, and global health/quality-of-life of EORTC QLQ-C30, LymS summary score of FACT-Lym, and EQ-5D-5L VAS will be summarized for the actual value and the change from baseline value at each scheduled assessment. For LymS summary score of FACT-Lym and EQ-5D-5L VAS, patients will be classified as improved/deteriorated based on the established clinically important differences for each measure. The proportion of patients with improvement/deterioration will be summarized.

Summary analyses will include data up to the start of subsequent anticancer therapy/procedure.

Data listing for each PRO questionnaire, including individual items and subscale items (if applicable), will be provided.

### **5.11.1 EORTC QLQ-C30**

The EORTC QLQ-C30 is a cancer health-related quality-of-life questionnaire (HRQoL) that has been widely used in clinical trials and investigations using PROs for individual patient management. It includes five functional domains (physical, emotional, social, role, and cognitive), eight symptoms (fatigue, pain, nausea/vomiting, constipation, diarrhea, insomnia, dyspnea, and appetite loss), as well as global health/quality-of-life and financial impact. Patients respond on a four-point scale from “not at all” to “very much” for most items. Most items use a “past week” recall period. Raw scores are linearly converted to a 0–100 scale with higher scores in functional and global health/quality-of-life scales reflecting better HRQoL and higher scores in symptom scales reflecting greater symptom burden. ([Snyder et al, 2013](#), and [EORTC QLQ-C30 Scoring Manual](#)).

Based on EORTC QLQ-C30 Scoring Manual (version 3.0), the subscale scores and the algorithm to linearly converted raw scores to a 0–100 scale are detailed below.

The rule to deal with missing items is summarized as below.

- Have at least half of the items from the scale been answered?
- If Yes, use all the items that were completed, and apply the standard equations given on the previous pages for calculating the scale scores; ignore any items with missing values when making the calculations.

- If No, set scale score to missing.
- For single-item measures, set score to missing.

The SAS program for scoring the QLQ-C30 and Modules is also in the manual.

Descriptive statistics (mean, standard deviation, median, and range) of the actual values of subscale scores and changes from baseline will be presented at each scheduled assessment.

### **5.11.2 EQ-5D-5L**

A change of 7 points in VAS from the baseline is considered the minimally important difference (MID) (Pickard et al., 2007). Patients will be classified as improved/deteriorated based on the established MID, i.e., if at least one of the post-baseline scores improves/deteriorates by the magnitude of the MID compared to baseline score. Proportion of patients with improvement/deterioration will be summarized.

Completion rate of the EQ-5D-5L will be calculated as the number of patients who complete at least one question of the EQ-5D-5L (e.g., either in descriptive system or VAS) divided by the number of patients treated at a visit. Summary of completion rate at each visit will be presented.

### **5.11.3 LymS of FACT-Lym**

Consisting of 15 items, LymS is a subscale of FACT-Lym questionnaire that addresses symptoms and functional limitations that are important to patients with non-Hodgkin lymphoma. The patient is asked to respond to each item with a score of 0–4, where 0 = not at all, 1 = a little bit, 2 = somewhat, 3 = quite a bit, and 4 = very much.

The FACT-Lym scoring guide identifies those negatively stated items that must be reversed before being added to obtain subscale totals. Negatively stated items are reversed by subtracting the response from “4”. After reversing proper items, all items in LymS are summed to a total. The higher score is associated with the better quality of life.

If  $\leq 50\%$  of item scores are missing, the subscale score will be calculated by multiplying the sum of the item scores by the number of items in the subscale, then divided by the number of non-missing item scores. This imputes the missing scores by the mean of the non-missing scores within a subscale.

LymS summary score = [sum of item scores]  $\times$  15/ [N of items answered]

The best change from baseline during the study, defined as the highest positive value among all post-baseline visits minus the baseline value, will also be summarized.

Based on anchor-methods, the thresholds of 4-point improvement and 5-point worsening will be considered as meaningful changes (Hlubocky et al., 2013). Patients will be classified as improved/deteriorated accordingly. Proportion of patients with improvement/deterioration will be summarized.

Completion rate of LymS will be calculated as the number of patients with sufficient number of items to calculate LymS summary score divided by the number of patients treated at a visit. Summary of completion rate at each visit will be presented.

## 6 Interim Analysis

In the non-GCB DLBCL cohort of Phase 2 when loncastuximab testirine is given intermittently, a Simon's 2-stage design will be used with an interim analysis for futility on the first 22 patients. If  $\geq 6$  patients achieve CR, this cohort will proceed to complete full enrollment. Enrollment will continue during the interim analysis; however, further enrollment in this cohort will be halted if futility is confirmed.

Further details are described in a separate document, Details of Futility Analysis, dated on 14 May, 2021. In the DLBCL cohort of Phase 2 when loncastuximab testirine is given at every cycle, a two-stage design with futility monitoring will be used for this new Phase 2 cohort. In the first stage, 60 patients will be accrued. If there are 20 or fewer CRs in these 60 patients, this cohort will be stopped. Otherwise, 40 additional patients will be accrued for a total of 100.

Further details are described in a separate document, Details of Two-Stage Design with Futility Monitoring, dated on yyyy-mm-dd.

## 7 Final Analysis

For primary and key secondary endpoints analyses, a database snapshot may be taken when 66 non-GCB DLBCL patients in Phase 2 have a minimum of 6 months follow up after initial documented response. All efficacy, safety, and PK endpoints will be analyzed and reported in the clinical study report (CSR). Results of the population PK analysis may be reported separately in a PK report. [REDACTED]

Follow-up analyses may be performed when all the patients complete the study per protocol.

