9.4 Final Analysis

For primary and key secondary endpoints analyses, a database snapshot may be taken when all patients have a minimum of 6 months follow up after initial documented response. All efficacy, and safety endpoints will be analyzed and reported in the clinical study report (CSR). Results of the PK analysis will be reported separately in a PK report.

Follow-up analyses may be performed when all the patients complete the study per protocol.

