### Phase 2:

Once the dose level of loncastuximab tesirine has been defined, the Phase 2 portion of the study will enroll in 3 separate cohorts: non-GCB DLBCL, GCB DLBCL, and MCL.

Each of the cohorts will be treated at the RP2D dose of loncastuximab tesirine determined in Phase 1 and ibrutinib. An IRC will be used in all cohorts to evaluate the response to the combination therapy.

Loncastuximab tesirine will be administered on C1D1 and C2D1. Patients who have a response of CR, PR, and SD at later disease assessments (Week 14 and Week 30) will receive additional doses of loncastuximab tesirine on C5D1, C6D1, C9D1, and C10D1. Ibrutinib will be administrated orally at 560 mg once daily continuously during all cycles. In the non-GCB DLBCL cohort, a Simon's 2-stage design will be used with an interim analysis for futility on the first 22 patients. If  $\geq 6$  patients achieve CR, this cohort will proceed to complete full enrollment. Enrollment will continue during the interim analysis; however, further enrollment in this cohort will be halted if futility is confirmed.

As of the data cutoff April 21, 2021, the interim analysis for non-GCB and GCB DLBCL cohorts was performed and the futility on non-GCB DLBCL was not met.

Subsequent to the interim analysis showing the potential of every cycle dosing of loncastuximab tesirine (see Protocol Section 2.2), the following will be performed:

- RP2D will be re-determined by DESC.
- Enrollment of the non-GCB DLBCL cohort treated with the combination of loncastuximab tesirine administered at an intermittent dose schedule and daily ibrutinib will be closed. GCB and MCL will complete the enrollment target set forth in the initial phase 2 design and remain under the initial treatment schedule.
- A new Phase 2 cohort of approximately 100 R/R DLBCL patients (with at least 40 patients each of GCB and non-GCB) will be introduced at the re-determined RP2D of loncastuximab tesirine administered in every cycle in combination with ibrutinib po daily given.

Patients will receive loncastuximab tesirine Q3W on Day 1 of first 2 cycles, followed by Q4W on Day 1 of every subsequent cycles. Ibrutinib will be administered at 560 mg po daily for first two cycles, then a dose reduction to 420 mg po daily for subsequent cycles.

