A two-stage design with futility monitoring will be used for this new Phase 2 cohort. In the first stage, 60 patients will be accrued. If there are 20 or fewer CRs in these 60 patients, this cohort will be stopped. Otherwise, 40 additional patients will be accrued for a total of 100.

The study will include a Screening Period (of up to 28 days), a Treatment Period (cycles of 3 to 4 weeks), and a Follow-up Period (approximately every 12-week visits for up to 2 years after treatment discontinuation). On March 3, 2022, ADC Therapeutics announced to discontinue the study. The new Phase 2 cohort will be not enrolled.

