## **Phase 2:**

89 patients will be treated during Phase 2 study.

The 89 patients will be treated with the combination of loncastuximab tesirine and ibrutinib in three different cohorts:

- 49 Non-GCB DLBCL was to enroll and treated interim data analysis for futility. The study will close with approximately 48 patients.
- GCB DLBCL cohort will enroll approximately 30 patients, and
- MCL cohort will enroll approximately 10 patients

Approximately 100 R/R DLBCL patients with at least 40 patients each for GCB and non-GCB will be accrued to the new treatment cohort where loncastuximab tesirine is given at every cycle with ibrutinib po daily.

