## **4.3 Modifications to the statistical section of the protocol**

Not applicable.

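### SAP 7 ties the main data snapshot to 66 Phase 2 non-GCB patients, but the closed cohort has 49; the condition cannot occur and differs from Protocol 9.4 without being declared

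*SAP*

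**What the plan says.** **Data cut.** SAP 7 allows the snapshot for the primary and key secondary endpoints "when 66 non-GCB DLBCL patients in Phase 2 have a minimum of 6 months follow up after initial documented response". Protocol 9.4 puts it differently: "a database snapshot may be taken when all patients have a minimum of 6 months follow up after initial documented response". SAP 4.3, headed "Modifications to the statistical section of the protocol", answers that none apply.

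**Cohort size.** SAP 4 (Phase 2) says that enrollment of the non-GCB cohort "administered at an intermittent dose schedule and daily ibrutinib will be closed". SAP 4.1 gives its size in one bullet, first as "49 Non-GCB DLBCL was to enroll and treated interim data analysis for futility" and then as "The study will close with approximately 48 patients". Protocol Table 5 closes the cohort at 48 of a planned 66.

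**Every-cycle cohort.** SAP 4.1 still says "Approximately 100 R/R DLBCL patients with at least 40 patients each for GCB and non-GCB will be accrued to the new treatment cohort". SAP 4, after reporting the March 2022 decision to discontinue, says "The new Phase 2 cohort will be not enrolled". SAP 4, 4.1 and 6 nevertheless keep its two-stage accrual in the future tense, and 4.1 keeps its 40-of-100 test.

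**Tests and primary analysis.** SAP 4.1 keeps the non-GCB test: reject at 20 or more complete responses in 66, with 90% power at a true CRR of 0.4. SAP 5.9 places the primary efficacy analysis in DLBCL patients treated at every cycle. SAP 5.9.1 plans the CRR with an exact 95% confidence interval and no test.

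**The concern.** The number in SAP 7 is the original design target, carried past the closure of the cohort. It is the only specific data-cut condition in the SAP, so a team following the document has no valid rule for timing the main analysis. A date chosen instead would not be pre-specified. The protocol's rule differs, and SAP 4.3, where a reader would look for an explanation, says there is nothing to declare.

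The same partial update leaves other text that a reader cannot safely interpret. The every-cycle cohort both will and will not be accrued, a hypothesis test is described for a sample size that was not reached, and the primary analysis that SAP 7 is meant to time has no patients.

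**Working it through.** **1. The plan's own design, at 66.** Inputs from SAP 4.1: continue if 6 or more of 22 respond completely; reject if 20 or more of 66 do; null CRR 0.2, alternative 0.4. The exact rejection probability is

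sum over x = 6 to 22 of P(Bin(22, p) = x) × P(Bin(44, p) ≥ 20 − x).

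- At p = 0.2: 0.0242, consistent with 0.05 two-sided (0.025 one-sided).
- At p = 0.4: 0.904, matching the stated 90%.

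The 66-patient design was sound. The fault is that the number was not updated.

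**2. Which non-GCB count the SAP uses.** SAP 4.1 gives 30 GCB, 10 MCL, 89 in Phase 2, 47 in Phase 1 and 136 in total.

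- With 49: 49 + 30 + 10 = 89, and 47 + 89 = 136. Both totals agree.
- With 48: 48 + 30 + 10 = 88, which does not.

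So 49 is the working figure.

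**3. Shortfall.** 66 − 49 = 17, or 17/66 = 26% of the condition (66 − 48 = 18 if the approximate figure is used).

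**4. Could other patients fill the gap?** The every-cycle cohort was to include at least 40 non-GCB patients, and 49 + 40 would exceed 66. But SAP 4 says the cohort will not be enrolled, and the total leaves no room for it: 136 − 47 − 89 = 0. Adding 100 would give 236. Phase 1 patients do not count either, because the sentence is limited to Phase 2.

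**5. Would the protocol's wording be enough?** Both documents count follow-up from first documented response. Read literally, a patient who never responds cannot meet that. Protocol 2.2 gives a non-GCB overall response rate of 45.5% among 22 patients at the April 2021 cutoff. That is 10 responders (10/22 = 45.5%) and 12 patients without a response. Copying the protocol's phrase would therefore replace one condition that cannot literally be met with another.

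**6. What the closed cohort supports.** The Clopper-Pearson 95% limits are the 2.5% quantile of Beta(x, n − x + 1) and the 97.5% quantile of Beta(x + 1, n − x). Near a 30% CRR:

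| Result | 95% CI | Half-width |
|---|---|---|
| 15/49 | 18.3% to 45.4% | 13.6 points |
| 20/66 | 19.6% to 42.9% | 11.6 points |

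**The case against.** The strongest reply is that this is leftover text with little effect. The snapshot may be taken but need not be, and SAP 7 separately allows follow-up analyses once all patients complete the study. SAP 1 and SAP 4 tell the reader that the study ended early and numbers were cut. SAP 5.9.1 already plans estimation only. Most of this stands: reporting is not blocked, and no planned estimate, interval or population changes.

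Two stronger readings are tempting and should be set aside. A reader might infer that the SAP credits the closed cohort with 90% power. It does not: SAP 4.1 attaches that power to the 66-patient design and claims none for 49. A reader might also see a substantive contradiction between 49 and approximately 48. The two are compatible, and the difference is editorial.

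What the reply does not answer is that a general notice of early termination does not say which sentences still apply. SAP 7 contains a specific number that cannot be reached, and SAP 4.3 says that nothing in the protocol's statistical section was modified.

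**Conclusion.** The point holds as an inconsistency in the current text. The SAP 7 condition is 17 patients out of reach, conflicts with Protocol 9.4 and is not declared in SAP 4.3. The superseded test, the every-cycle accrual text and the primary analysis in SAP 5.9 have the same cause.

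The severity is minor to should-fix. The rule is wrong as written and easy to correct, but the analysis can go ahead without it. The documents do not support saying that the trial cannot be reported, or that a new rejection cutoff is needed. No analysis section plans a test for the non-GCB cohort, and its first 22 results (6 complete responses) were known before the cohort closed.

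The conclusion rests on 49 being the cohort size, as the SAP totals imply, and on the cohort staying closed. The interval at 15/49 is illustrative. It also assumes that all 49 are in the Efficacy Analysis Set, whose size the documents do not give.

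**What to change.** 1. **SAP 7.** Replace the reference to 66 Phase 2 non-GCB patients with all treated patients. State that responders need at least 6 months of follow-up after first response unless they progressed, died or left the study earlier. State that non-responders count once they have progressed, died, left the study or completed their planned assessments. Record this in SAP 4.3, because it adds to Protocol 9.4.
2. **SAP 4, 4.1 and 6.** Use 49 as the single non-GCB count. Mark the every-cycle accrual and test text as not enrolled.
3. **SAP 4.1, non-GCB justification.** Label the 66-patient test and its power as the original design, not completed because of early closure. State that the CRR is reported with its exact 95% confidence interval only, as in SAP 5.9.1.
4. **SAP 5.9.** State that the every-cycle primary analysis will not be done because no patients were enrolled, and that the CRR in the enrolled cohorts is secondary and descriptive.
5. **SAP 4.3.** List changes 2 to 4 as departures from Protocol 9.1.1 and 9.1.2 and from the primary endpoint in Protocol Section 3.

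The cost is SAP wording only, with no new data or analyses. The trial would openly report no Phase 2 primary result and no formal non-GCB test. The non-GCB CRR would be read as an estimate with a half-width of about 13.6 points near 30%.

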## 8 Data handling conventions

### 8.1 General conventions

#### 8.1.1 Missing data

In general, missing data including dates will be treated as missing and no data imputation will be applied, unless otherwise specified. Data that are potentially spurious or erroneous will be queried and examined during the review of the study data.

If there are partial or missing dates for an AE, then it will be considered as a TEAE. If the assessment of the relationship of an AE to study drug is missing, then the relationship will be as possibly related.

If the severity/grade is missing for one of the treatment emergent occurrences of an AE, the maximal severity of the remaining occurrences will be considered. If the severity is missing for all the occurrences a “missing” category will be added in summary table.

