8.2.2 Eliciting and Reporting Adverse Events/Serious Adverse Events

Patients will be instructed to contact the Investigator at any time after ICF signature if any symptoms develop. At each study visit, patients will be asked a non-leading question to elicit any medically related changes in their well-being. Patients may also report AEs voluntarily and they will be instructed to contact the Investigator between visits if any symptoms develop or worsen.

Adverse events (AEs) will be reported starting when the patient provides written informed consent. Clinically significant medical conditions present at the time of ICF signature will be reported as medical history. Clinically significant medical conditions that start or worsen after ICF signature will be reported as AEs.

All AE/SAEs, regardless of relationship to study drug, will be reported from the time the patient signs the ICF until 30 days after the last dose of study drug or the start of a new anti-cancer therapy, whichever occurs earlier; thereafter, only related SAEs will be reported with two exceptions:

1. Patients who have responded to loncastuximab tesirine and undergo SCT (either autologous or allogeneic) after permanent discontinuation of loncastuximab tesirine treatment without any intervening anti-cancer therapy. These patients will have the following safety information reported until 180 days' post-transplant regardless of relationship to loncastuximab tesirine:
 - a. Grade ≥ 3 AEs suggestive of hepatic toxicity, veno-occlusive disease/sinusoidal obstruction syndrome, graft-versus-host disease, infectious complications, prolonged cytopenia(s), and pulmonary toxicity
 - b. SAEs
 - c. Death
2. Patients who receive CAR-T therapy after permanent discontinuation of loncastuximab tesirine treatment will have the following safety information reported until 90 days after receiving CAR-T therapy regardless of relationship to loncastuximab tesirine:
 - a. Grade ≥ 3 AEs of cytokine release syndrome, encephalopathy, edema or effusion, rash, hepatic toxicity
 - b. SAEs
 - c. Death

Whenever possible, AEs should be reported as a diagnosis rather than individual signs and symptoms. If no diagnosis is available or has been identified, then the primary symptom is reported.

In general, the term 'disease progression' should not be used for reporting an AE/SAE. However, AEs/SAEs that are complications of disease progression should be reported.

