9.8.1 Adverse Events

The focus of AE summarization will be on TEAEs. A TEAE is defined as an AE that occurs or worsens in the period extending from the first dose of study drug to 30 days after the last dose of study drug or initiation of new anti-cancer therapy (whichever occurs first).

The TEAEs will be summarized. Summary tables will be presented to show the number of patients reporting TEAEs by severity grade and corresponding percentages. A patient who reports multiple TEAEs within the same Preferred Term (or System Organ Class) is counted only once for that Preferred Term (or System Organ Class) using the worst severity grade.

Separate summaries will be prepared for TEAEs classified as severe or life-threatening (Grade 3 or higher); study drug-related AEs; AEs leading to treatment interruption, modification, or discontinuation; SAEs; AESIs; and death.

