### **5.10.1 Adverse Events**

#### **5.10.1.1 Analyses of Adverse Events**

An AE is defined as any untoward medical occurrence in a patient or clinical investigation subject administered a pharmaceutical product, which does not necessarily have to have a causal relationship with this treatment.

The definition of SAEs is referred to the Protocol section 8.2.1.

A treatment-emergent AE (TEAE) is defined as an AE that occurs or worsens in the period extending from the first dose of study drug to 30 days after the last dose of study drug in this study or start of a new anticancer therapy, whichever is earlier.

AEs will be coded according to MedDRA Version 22.0, and the severity of the toxicities will be graded according to the National Cancer Institute (NCI) Common Terminology Criteria for Adverse Events (CTCAE) Version 4.0, where applicable.

The summary of overall TEAEs includes:

- TEAEs
- Drug-related TEAEs (loncastuximab tesirine or ibrutinib)
- Grade  $\geq 3$  TEAEs
- Drug-related Grade  $\geq 3$  TEAEs (loncastuximab tesirine or ibrutinib)
- Serious Adverse Events (SAEs)
- Drug-related SAEs (loncastuximab tesirine or ibrutinib)
- TEAEs leading to dose delayed, reduced or interrupted (loncastuximab tesirine or ibrutinib)
- TEAEs leading to discontinuation of loncastuximab tesirine or ibrutinib
- TEAEs leading to death
- Infusion related reactions

The incidence of TEAEs will be summarized by system organ class (SOC) and preferred term (PT). A patient will be counted only once within a SOC and PT, even if the patient experienced more than one AE within a specific SOC and PT. Below TEAEs will be summarized in the same fashion:

- Drug-related TEAEs by SOC and PT
- Grade  $\geq 3$  TEAEs by SOC and PT
- Drug-related Grade  $\geq 3$  TEAEs by SOC and PT
- The most common TEAEs ( $\geq 10\%$  incidence) by PT
- TEAEs by SOC, PT and maximum CTCAE grade
- TEAEs by relationship to loncastuximab tesirine or ibrutinib, maximum CTCAE grade, SOC and PT

Listings of all AEs, including non-TEAEs, will be provided. Besides, TEAEs leading to dose reduced, delayed or interrupted (loncastuximab tesirine or ibrutinib), TEAEs leading to discontinuation of loncastuximab tesirine or ibrutinib, and TEAEs leading to death will also be provided.

Details on classification of AEs with missing or partial onset dates are provided in Section 6.

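### The SAP's missing-date rule makes an AE treatment-emergent even when the known part of its dates places it outside the TEAE window (minor)

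*SAP*

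**What the plan says.** SAP 8.1.1 starts from a general position: "In general, missing data including dates will be treated as missing and no data imputation will be applied, unless otherwise specified". For adverse events it then gives one specific rule: "If there are partial or missing dates for an AE, then it will be considered as a TEAE". The rule has no condition attached, and it does not say which date it means.

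SAP 5.10.1.1 defines a TEAE by timing. The test is whether the event "occurs or worsens in the period extending from the first dose of study drug to 30 days after the last dose of study drug", with an earlier close if a new anticancer therapy starts. Protocol 9.8.1 uses the same window. SAP 4.3 records no departure from the protocol's statistical section, so the date rule was not announced as a change to that definition.

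SAP 5.10.1.1 also tells the reader: "Details on classification of AEs with missing or partial onset dates are provided in Section 6". Section 6 of the SAP is Interim Analysis and says nothing about AE dates.

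On collection, Protocol 8.2.2 says: "Adverse events (AEs) will be reported starting when the patient provides written informed consent". After the main reporting period it keeps related SAEs. It also keeps selected Grade 3 or higher events, SAEs and deaths for 180 days after a stem cell transplant and 90 days after CAR-T therapy.

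**The concern.** A default for unknown timing should operate only where timing is unknown. Here it also operates where the record settles the question. An event with onset in a month wholly before first dose, or wholly after the window closed, did not arise in the window, yet the rule puts it there because the day is blank. The same happens to an event with no onset date that ended before first dose.

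AE and SAE frequency and severity is one of the Phase 1 primary endpoints and a Phase 2 secondary endpoint, and Protocol 9.8.1 makes TEAEs the focus of AE summaries. The SAP keeps TEAEs apart from other AEs: it lists non-TEAEs, and it summarizes SAEs and AESIs both as TEAEs and as post-dose AEs. The rule moves events across that line in one direction only, towards more TEAEs.

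The plural, unqualified word for dates also leaves open whether a missing end date triggers the rule.

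**Working it through.** The plan gives no figure to reproduce. The check sets the rule against the definition and then bounds the effect of one misclassified patient.

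**Step 1: is there a finer rule elsewhere?** The only pointer (SAP 5.10.1.1) leads to Section 6, which has no such rule. Section 8.1.1 is therefore the only operative text.

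**Step 2: can out-of-window AEs be in the database?** Yes. Screening lasts up to 28 days and AEs are reported from consent. Related SAEs and the transplant and CAR-T exceptions extend beyond the window.

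**Step 3: rule against definition.** For illustration only, assume first dose on 10 March 2021, last dose on 20 June 2021 and no new anticancer therapy. The window then closes on 20 July 2021 (20 June + 30 days). For each record, take the earliest and latest dates consistent with what is known.

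| Record | Could onset lie in the window? | SAP 8.1.1 |
|---|---|---|
| Onset February 2021, day missing | No | TEAE |
| Onset 2020, year only | No | TEAE |
| Onset September 2021, day missing | No | TEAE |
| Onset missing, ended 5 March 2021 | No | TEAE |
| Onset 1 March 2021 complete, end date missing | No | TEAE, if end dates count |
| Onset March 2021, day missing | Yes | TEAE |
| Onset missing, ended 1 April 2021 | Yes | TEAE |

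Four records are misclassified on any reading of the rule. A fifth is misclassified only if the rule covers end dates. The last two are truly ambiguous, and TEAE is the usual conservative answer. The year-only record shows the logic; with screening limited to 28 days, it would normally arise only where screening spans a new year. A pre-dose event that worsens inside the window is a TEAE by definition, so the misclassification concerns events without such worsening.

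**Step 4: ceiling per patient.** One patient adds at most 100 × 1/N percentage points to a row. The N are from SAP 4.1; GCB and MCL are approximate.

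- All patients: 100 × 1/136 = 0.7
- Phase 1: 100 × 1/47 = 2.1
- Non-GCB, Phase 2: 100 × 1/49 = 2.0 (SAP 4.1 also gives about 48; 100 × 1/48 = 2.1)
- GCB, Phase 2: 100 × 1/30 = 3.3
- MCL, Phase 2: 100 × 1/10 = 10

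A patient counts once per system organ class and preferred term, so the increase is zero where that patient already has a TEAE in the row. Phase 1 safety tables are also broken down by dose level, with smaller denominators that the SAP does not state.

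**The case against.** The strongest reply is that the rule is a conservative convention. It can only over-count, and it matches the next sentence of 8.1.1, which treats a missing relationship as possibly related. Exposure is narrow: conditions present at consent are medical history, screening is short, late collection is confined to selected events, and SAEs must be reported within 24 hours of site awareness. Late SAEs and AESIs appear in the post-dose summaries anyway, and all AEs are listed. This all stands and is why the point is minor. It does not justify applying the default where the known dates already give the answer.

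Four stronger readings are tempting but are not supported:

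- *Every ongoing pre-dose AE becomes a TEAE.* The wording permits this but does not establish it. The pointer in SAP 5.10.1.1 speaks of onset dates, and Protocol 8.2.2 records ongoing as a status in place of a resolution date. This is an ambiguity to close. A missing end date says nothing either way about emergence.
- *The rule attributes screening or post-CAR-T events to the study drugs.* TEAE status concerns timing. Relatedness is a separate investigator assessment with its own tables.
- *TEAE incidence is the Phase 1 primary endpoint.* The endpoint is AE and SAE frequency and severity, one of four. DLTs have their own definition, period and analysis set, and the rule does not enter that count.
- *The 1/N figures estimate the bias.* They are ceilings for one patient in one row.

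**Conclusion.** The point holds as a minor correction. As written, SAP 8.1.1 gives a wrong classification for AEs whose known onset month or year, or complete end date before first dose, lies outside the SAP's own window, and no other text overrides it. The direction is over-counting of TEAEs in descriptive tables. The total size cannot be estimated, because the documents do not give the number of partial dates. This conclusion assumes that the programmer applies 8.1.1 literally and that at least some out-of-window AEs have incomplete dates. If none do, no table changes.

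**What to change.** Replace the sentence in SAP 8.1.1 with:

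*An AE with a missing or partial onset date is considered a TEAE unless the known part of the onset date shows onset before first dose or after the end of the TEAE window, or a complete end date is before first dose. An AE with onset before first dose that is recorded as worsening within the TEAE window remains a TEAE. A missing end date does not affect TEAE status.*

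In SAP 5.10.1.1, change the cross-reference from Section 6 to Section 8.1.1.

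The cost is a short SAP text change, one corrected pointer and a few lines of code. No new data are needed, and the conservative default stays wherever the known dates leave the timing open.
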